5.5 Overdose and Toxicity

CTAP101 Capsules contain calcifediol, which is a vitamin D metabolite. An increased serum calcium has been shown to be one of the first indicators of toxicity associated with vitamin D overdose and is frequently used as a surrogate marker of toxicity in patients treated with vitamin D therapy. Progressive hypercalcemia may require emergency attention. Acute hypercalcemia may exacerbate tendencies for cardiac arrhythmia and seizure, and may potentiate the action of digitalis. Chronic or repeated hypercalcemia can lead to generalized vascular and soft tissue calcification.

No specific antidote to CTAP101 Capsules exists. If overdose is suspected, the subject should be monitored closely and kept under observation by a physician. The $t_{1/2}$ of calcifediol is approximately 30 days in adult patients with stage 3 or 4 CKD. Possible clinical and laboratory events include hypercalcemia and hypercalciuria.

5.6 Method of Assigning Subjects to Treatment Groups

After signing the ICF, prior to any study-related activities, subjects will be assigned a site-generated, ascending subject identification number and will retain that number throughout the study. Should a subject be withdrawn from the study, the subject identification number will not be reassigned. Approximately 350 subjects will be screened to enroll approximately 108 subjects who meet the enrollment criteria.

An IRS will provide study treatment group assignments for these 108 subjects using the computer-generated randomization code provided by the IRS vendor. The randomization code will be stratified age group (8 to <12 years and 12 to <18 years) and balanced within each age group for gender and CKD stage (stages 3 and 4).

In Cohort 1 (ages 12 to <18 years), approximately 72 subjects, balanced for gender and CKD stage, will be randomized in a 2:1 ratio to active or placebo treatment, respectively. Ten (10) subjects will be randomly selected from the active group and five (5) subjects will be randomly selected from the placebo group for intensive PK evaluation during the last 3 days of the 12th week of treatment (prior to dose escalation). Twenty other subjects will be randomly selected for end of study PK evaluations from the active group, ten of which will be receiving an end of study dose of 30 mcg/day and the other ten will receiving an end of study dose of 60 mcg/day.

In Cohort 2 (ages 8 to <12 years), approximately 36 subjects, balanced for gender and CKD stage, will be randomized in a 2:1 ratio to active or placebo treatment, respectively. Ten (10) subjects will be randomly selected from the active group and five (5) subjects will be randomly selected from the placebo group for intensive PK evaluation during the last 3 days of the 12th week of treatment (prior to dose escalation). End of study PK evaluations will be made after 26 weeks of treatment. Twenty other subjects will be randomly selected for end of study PK evaluations from the active group, ten of which will be receiving an end of study dose of 30 mcg/day and the other ten will receiving an end of study dose of 60 mcg/day.

For both cohorts, an IRS will provide study treatment group assignments using the computer-generated randomization code.

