Blood samples will be collected at weekly, biweekly or monthly intervals during the 10-week pre-treatment screening/baseline period, the 26-week treatment period and the 6-week post-treatment FU period. Sparse PK samples will be collected from all subjects on Day 83 at 0 (pre-dose), 6, 12, 24 hours (Day 84 pre-dose) and 48 hours (Day 85 pre-dose). Additional PK blood samples will be collected in both Cohort 1 and Cohort 2 in subsets of 10 subjects treated with CTAP101 Capsules and 5 subjects treated with placebo during the last 3 days of the 12th week of treatment (prior to dose titration). The additional PK samples will be collected as follows: Day 83: -2, 2, 4 and 8 hours. End of study PK blood samples will be collected in other subsets of approximately 20 subjects (20 subjects from each cohort) during the post-treatment FU period. In each cohort, an attempt will be made to collect PK samples from 10 subjects on each ending daily dose level (30 or 60 mcg) of CTAP101 Capsules, in order to establish the terminal elimination half-lives ($t_{1/2}$) of 25-hydroxyvitamin D₃ at each of these dose levels.

[figure not shown]
All subjects, study personnel and the sponsor will be blinded to the administered treatments and to plasma iPTH, serum total 25-hydroxyvitamin D and serum 25-hydroxyvitamin D₃ data until the last subject completes 26 weeks of treatment. Unblinded data will be provided to all study sites when the final clinical study report becomes available.

An interim analysis of data obtained from the 15 subjects in Cohort 1 who provide intensive PK samples during the last three days of treatment week 12 will be undertaken by the DSMB to determine the appropriate starting dose for Cohort 2. A second interim analysis of data obtained from 15 subjects in Cohort 2 who provide intensive PK samples during the last three days of treatment week 12 will be undertaken by the DSMB to determine the appropriate starting dose for a separate phase 2 study in subjects of ages 1 month to <8 years.

A diagram of the study design for Cohort 1 (n=~72) is shown below:

A diagram of the study design for Cohort 2 (n=~36) is shown below:

Duration of Study:

Each subject will participate in the study for up to approximately 42 weeks (2-weeks screening/baseline, 8-weeks washout, if required, 26-weeks of treatment with CTAP101 Capsules or matching placebo, and 6-weeks of FU evaluation).

Study Parameters:

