Key parameters to be monitored at regular intervals during the study include: plasma iPTH, serum calcium (corrected for serum albumin), serum phosphorus, serum CaxP product, serum total 25-hydroxyvitamin D, serum 25-hydroxyvitamin D₃, and urine calcium:creatinine ratio. Vital signs (VS) and adverse events (AEs) will be monitored at each study visit. Other parameters to be monitored less frequently include brief physical examinations (PEs), clinical laboratory tests (hematology and clinical and urine chemistries) and patient-reported palatability and acceptability. Twelve-lead electrocardiograms (ECGs) will be obtained at baseline and at the end of treatment or ET. [REDACTED]

[figure not shown]
[REDACTED] All subjects, study personnel and the sponsor will be blinded to the administered treatments and to plasma iPTH, serum total 25-hydroxyvitamin D and serum 25-hydroxyvitamin D₃ data until the last subject completes 26 weeks of treatment. Unblinded data will be provided to all study sites when the final clinical study report becomes available.

Blood samples will be collected at weekly, biweekly or monthly intervals during the 10-week pre-treatment screening/baseline period, the 26-week treatment period and the 6-week post-treatment FU period. Sparse PK samples will be collected from all subjects on Day 83 at 0 (pre-dose), 6, 12, 24 hours (Day 84 pre-dose) and 48 hours (Day 85 pre-dose). Additional PK blood samples will be collected in both Cohort 1 and Cohort 2 in subsets of 10 subjects treated with CTAP101 Capsules and 5 subjects treated with placebo during the last 3 days of the 12th week of treatment (prior to dose titration). The additional PK samples will be collected as follows: Day 83: -2, 2, 4 and 8 hours. End of study PK blood samples will be collected in other subsets of 20 subjects (20 subjects from each cohort) during the post-treatment FU period, 10 subjects on each ending daily dose level (30 or 60 mcg) of CTAP101 Capsules, in order to establish the $t_{1/2}$ of serum 25-hydroxyvitamin D₃ at each of these dose levels.

[figure not shown]
All subjects, study personnel and the sponsor will be blinded to the administered treatments and to plasma iPTH, serum total 25-hydroxyvitamin D and serum 25-hydroxyvitamin D₃ data until the last subject completes 26 weeks of treatment.

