5.7 Blinding

An IRS will provide study treatment group assignments (using a computer-generated randomization code provided by the IRS vendor) and dosing adjustments. An independent, unblinded DSMB will oversee the IRS and verify the appropriateness of all dosing adjustments, and monitor subject safety and the effectiveness of CTAP101 Capsules at regular intervals. Members of the DSMB will also conduct periodic reviews of study conduct to verify that all required data are captured to a sufficiently high degree (>95%) and within specified time frames (usually within 5 days), and to promptly recommend appropriate corrective actions to address any noted deficiencies, in an effort to minimize missing data. Specific responsibilities and activities of the DSMB will be defined in the charter ratified at the pre-study organizational meeting. These responsibilities will include the completion of an interim analysis of the repeated-dose PK data obtained during treatment week 12 in Cohort 1 to justify a starting dose for Cohort 2.

All subjects, site research staff and sponsor will be blinded as to whether a given subject is in the CTAP101 Capsules or placebo treatment group until after database lock or until the decision to break the blind is determined (eg, as a result of an emergent event, SUSAR). When the primary investigator determines that knowledge of treatment group assignment is required for medical management of an individual subject, the sponsor will be contacted immediately. The blind for the subject will be broken using the IRS system.

Further, all subjects, site research staff and sponsor will be blinded to the administered treatments and plasma iPTH, serum total 25-hydroxyvitamin D, and serum 25-hydroxyvitamin D₃ laboratory data until the last subject completes 26 weeks of treatment. Unblinded data will be provided to all study sites when the final clinical study report becomes available.

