A central laboratory experienced in clinical research studies will be utilized. Collection, processing, storage and shipping procedures will be performed in accordance with the instructions provided by the central laboratory. Detailed instructions will be provided separately from this protocol in the laboratory manual. Blood samples will be collected and analyzed for clinical laboratory [REDACTED] tests. Approximately 357 mL of blood will be collected over the entire duration of the study from each of the 15 subjects who provide intensive PK samples during the last three days of treatment week 12. Approximately 373 mL of blood will be collected over the entire duration of the study from each of the 20 subjects who provide PK samples during the post-treatment FU period. Approximately 323 mL of blood will be collected over the entire duration of the study from all other subjects.

Additional blood draws may be needed for unscheduled or repeat visits. Given the nature of this pediatric patient population, care should be taken with the amount of blood drawn at any one study visit or cumulative over a four week period.

[REDACTED]

[REDACTED]

[REDACTED]

Samples are to be shipped to the central laboratory for each subject as visits are completed. The investigator will provide a limited access, and a -20°C or lower freezer space for respective serum and plasma aliquots.

6.4.3 *Clinical Supplies*

The sponsor or assigned designee will supply vacutainers, blood collection tubes, labels, boxes with labels for storage of serum and plasma samples and all necessary shipping supplies/containers. The investigator will supply all phlebotomy and centrifugation equipment including biohazard and/or safety supplies. The investigator will ensure that all biohazard wastes are disposed of in accordance with investigator site standard operating procedures (SOPs) and local regulations.

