7.3 Follow-up Period or Second PK Assessment

7.3.1 *Visit 23 (Day 190)*

- Must occur on the scheduled day
- Required only for subjects participating in the second PK assessment
- AE Assessment

- Concomitant medications
- VS measurements
- Blood samples drawn for:
 - Chemistry (partial panel)
 - Serum 25-hydroxyvitamin D₃, [REDACTED]

7.3.2 *Visit 24 (Day 197)*

- May occur ± 3 day of scheduled day
- Required only for subjects participating in the second PK assessment
- Concomitant medications
- AE assessment
- VS measurements
- Blood samples drawn for:
 - Chemistry (full panel) and hematology
 - Plasma iPTH
 - Serum total 25-hydroxyvitamin D
 - Serum 25-hydroxyvitamin D₃, [REDACTED]

7.3.3 *Visits 25-27 (Days 204-218)*

- Must occur on the scheduled days
- Required only for subjects participating in the second PK assessment
- AE Assessment
- Concomitant medications
- VS measurements
- Blood samples drawn for:
 - Chemistry (partial panel)
 - Serum 25-hydroxyvitamin D₃, [REDACTED]

7.3.4 *Visit 28/ET (Day 225)*

- May occur ± 3 day of scheduled day
- Concomitant medications
- AE assessment
- PE (including weight, height and BMI)
- VS measurements
- 12-lead ECG

- Urine chemistry and urinalysis
- Urine pregnancy (only for females of childbearing potential)
- Blood samples drawn for:
 - Chemistry (full panel) and hematology
 - Plasma iPTH
 - Serum total 25-hydroxyvitamin D
 - Serum 25-hydroxyvitamin D₃, [REDACTED]
 - [REDACTED]

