9.2 Determination of Sample Size

Sample size has been calculated (using Fisher's exact test statistics) to provide power of 80% for a two-sided, alpha 0.05 level test of equal proportions comparing the percentages of subjects attaining a mean decrease of at least 30% in plasma iPTH (averaged over the last 6 weeks of treatment) compared to baseline on daily dosages of CTAP101 Capsules (active) versus placebo. Assuming response rates of at least 0.4 (CTAP101 Capsules) versus 0.1 (placebo), and using a 2:1 ratio of CTAP101 Capsules:placebo subjects with an estimated 20% dropout rate over the course of the study, a sample size of approximately 108 subjects is required in the study with two-thirds apportioned to the 12 to <18 year age group (Cohort 1) and one-third apportioned to the 8 to <12 year age group (Cohort 2), allocated as 72 subjects to CTAP101 Capsules and 36 subjects to placebo.

No subject replacement is planned.

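### Cohort 2 cannot supply its stated PK subsets: they need 30 distinct active subjects, and about 36 subjects randomized 2:1 give about 24

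*Combined protocol and SAP*

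**What the plan says.** Section 5.6 sets the size of Cohort 2: "approximately 36 subjects, balanced for gender and CKD stage, will be randomized in a 2:1 ratio to active or placebo treatment". From the active arm it draws 10 subjects at random for intensive PK sampling in the last three days of week 12, with 5 more from placebo. Its rule for the end-of-study subset then reads: "made after 26 weeks of treatment. Twenty other subjects will be randomly selected for end of study PK evaluations from the active group". Half are to finish on 30 mcg/day and half on 60 mcg/day, which is 10 at each dose. The Cohort 1 paragraph asks for the same numbers.

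Section 3.1 states the same size firmly, placing the sampling "in other subsets of 20 subjects (20 subjects from each cohort) during the post-treatment FU period, 10 subjects on each ending daily dose level". The Synopsis is softer. It says approximately 20 per cohort, and for the dose split: "In each cohort, an attempt will be made to collect PK samples from 10 subjects on each ending daily dose level". Section 6.4.2 gives one blood volume for the 15 intensive-PK subjects and a different one "from each of the 20 subjects who provide PK samples during the post-treatment FU period", so it treats the two groups as separate.

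Section 9.2 assumes 20% dropout, allocates 72 subjects to active and 36 to placebo overall, and adds: "No subject replacement is planned". Sections 2.1.1 and 3.1 make the PK profile in ages 8 to <18 a primary objective and give half-life at each ending dose as the purpose of the follow-up subset.

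**The concern.** The word *other* in the Synopsis and in Sections 3.1 and 5.6 makes the two subsets disjoint. The active arm of Cohort 2 must therefore be large enough for both, and it appears smaller than their sum.

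If so, whoever programs the selection cannot follow the protocol and will have to improvise. The plan would also promise a Cohort 2 half-life sample that the cohort cannot reach.

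Two further conflicts arise from the same sentence in Section 5.6:

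- **Blinding.** The end-of-study subset comes from the active group only, and Section 7.3 marks Visits 23 to 27 as "Required only for subjects participating in the second PK assessment". Under Section 5.7, subjects, "site research staff and sponsor will be blinded as to whether a given subject is in the CTAP101 Capsules or placebo treatment group" until database lock. A call to those visits therefore identifies active treatment. If every available active subject were called to get nearer to 20, a completer outside the intensive subset who is not called would be identifiable as placebo.
- **Ending doses.** Section 5.6 names 30 and 60 mcg/day for Cohort 2, while Section 5.3 leaves the Cohort 2 starting dose to the interim analysis. The two conflict if that analysis selects a different starting dose.

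**Working it through.** **Inputs.** Cohort sizes about 72 and about 36, allocation 2:1, 10 intensive-PK active subjects and 20 other end-of-study active subjects per cohort (Section 5.6); 72 active and 36 placebo overall, 20% dropout, no replacement (Section 9.2).

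**Reproducing the plan's allocation.** Active = N × 2/3.

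- Cohort 1: 72 × 2/3 = 48.
- Cohort 2: 36 × 2/3 = 24.
- Sum: 48 + 24 = 72, which agrees with Section 9.2.

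**Demand against supply**

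| | Cohort 1 | Cohort 2 |
|---|---|---|
| Active subjects needed (10 + 20) | 30 | 30 |
| Active subjects available | 48 | 24 |
| Others after removing 10 | 38 | 14 |
| Others completing at 20% dropout | 38 × 0.8 = 30.4 | 14 × 0.8 = 11.2 |

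Cohort 2 is 30 − 24 = 6 active subjects short before any dropout. An even split of 14 gives 7 per dose. If dropout is taken instead as 10% or 30% (assumed range), expected completers among the 14 are 12.6 or 9.8.

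**Cohort 2 size that the stated subsets would need**

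- No dropout: 30 × 3/2 = 45.
- 20% dropout among the 20 others: 20/0.8 = 25, and (10 + 25) × 3/2 = 52.5, so about 53.

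**If overlap were allowed.** All 24 active subjects become eligible, and 24 × 0.8 = 19.2 are expected to complete. With independent dropout (an assumption):

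- P(Bin(24, 0.8) ≥ 20) = 0.46.
- P(Bin(24, 0.8) ≥ 18) = 0.81.
- At 10% dropout, the chance of at least 20 rises to 0.91.

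For at least ten completers on each dose, the probability is summed over 20 to 24 completers. The documents give no titration rate, so the splits are assumed: 0.14 at 50:50, 0.10 at 40:60 and 0.03 at 30:70. This treats every completer as ending on one of the two doses. Section 5.4 allows up to four reductions, so some may end on neither.

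**The case against.** The arithmetic is not in dispute. The objections concern its weight and the remedy.

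- **The wording is already soft.** The Synopsis says approximately 20, and Section 9.8.3 gives half-life as feasible. But the attempt in the Synopsis covers only the dose split, Sections 3.1 and 5.6 are unqualified, and 14 is not approximately 20. The feasibility clause covers calculating the parameter, not drawing the sample.
- **Cohort 2 is only approximately 36.** This is fair: 14 means about 14. It does not close the gap, because 45 is 25% above 36.
- **Allowing overlap would nearly solve it.** The strongest point. With 19.2 completers expected, the Synopsis figure would be roughly met, though ten per dose would remain unlikely. The text excludes overlap, and overlap would add to the blood drawn from the same child. The sponsor may choose it, but must then say so.
- **The dose-split probabilities rest on invented splits.** They are illustrative only, and the conclusion does not need them.
- **Little is exposed by the blinding conflict.** The calls come after a subject's Day 183 visit, when that subject's efficacy samples are complete, so the primary endpoint is largely protected. Adverse events are still collected until 30 days after the last dose, with relatedness judged by the investigator. The conflict also applies to Cohort 1.
- **The samples taken from everyone are thin support.** Day 183 and Day 225 are two points 42 days apart, against an adult half-life of about 30 days (Section 3.2). They help but do not replace the subset.

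**Conclusion.** The concern holds. In Cohort 2 the stated subsets need 30 distinct active subjects and about 24 will exist. At most about 14 can enter the end-of-study subset, with about 11 expected to complete. The first two figures follow from the protocol's own numbers; the third assumes that the study-wide 20% dropout applies to this group.

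The consequence is limited. No hypothesis test or power statement depends on the 20. Primary efficacy, the Day 83 to 85 PK and both interim analyses are unaffected, and Cohort 1 can meet its numbers. What the design cannot deliver is the stated sample for half-life by ending dose in ages 8 to <12. This should be corrected before the selection is programmed; it does not call the trial's main conclusion into question.

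**What to change.** 1. Restate the Cohort 2 end-of-study PK sample as an attainable number: up to about 14 distinct active subjects, with about 11 expected to complete. Drop the fixed ten per dose and report the number achieved at each ending dose. If the sponsor prefers overlap with the intensive subset, say so explicitly, with about 19 expected completers and the added blood volume.
2. Make the Synopsis and Sections 3.1, 5.6 and 6.4.2 agree on that number.
3. State that half-life by dose in Cohort 2 will be estimated as feasible, also using the Day 183 and Day 225 samples already scheduled for all subjects.
4. Specify how subjects are called to Visits 23 to 27 so that neither being called nor not being called reveals allocation before unblinding.
5. Reconcile the Cohort 2 ending doses in Section 5.6 with Section 5.3.

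**Cost.** Mostly wording, and a smaller stated PK sample for Cohort 2. If masking is achieved by also calling placebo subjects, each has five extra visits and about 373 − 323 = 50 mL more blood. Cohort 2 has about 36/3 − 5 = 7 placebo subjects outside the intensive subset, so the number called should be kept small or another masking method used.

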5.7 Blinding

An IRS will provide study treatment group assignments (using a computer-generated randomization code provided by the IRS vendor) and dosing adjustments. An independent, unblinded DSMB will oversee the IRS and verify the appropriateness of all dosing adjustments, and monitor subject safety and the effectiveness of CTAP101 Capsules at regular intervals. Members of the DSMB will also conduct periodic reviews of study conduct to verify that all required data are captured to a sufficiently high degree (>95%) and within specified time frames (usually within 5 days), and to promptly recommend appropriate corrective actions to address any noted deficiencies, in an effort to minimize missing data. Specific responsibilities and activities of the DSMB will be defined in the charter ratified at the pre-study organizational meeting. These responsibilities will include the completion of an interim analysis of the repeated-dose PK data obtained during treatment week 12 in Cohort 1 to justify a starting dose for Cohort 2.

All subjects, site research staff and sponsor will be blinded as to whether a given subject is in the CTAP101 Capsules or placebo treatment group until after database lock or until the decision to break the blind is determined (eg, as a result of an emergent event, SUSAR). When the primary investigator determines that knowledge of treatment group assignment is required for medical management of an individual subject, the sponsor will be contacted immediately. The blind for the subject will be broken using the IRS system.

Further, all subjects, site research staff and sponsor will be blinded to the administered treatments and plasma iPTH, serum total 25-hydroxyvitamin D, and serum 25-hydroxyvitamin D₃ laboratory data until the last subject completes 26 weeks of treatment. Unblinded data will be provided to all study sites when the final clinical study report becomes available.

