1.13 Clinical Efficacy and Safety

In CTAP101-CL-2008, a double-blind, placebo-controlled, randomized repeat-dose study, daily administration of CTAP101 Capsules increased serum total 25-hydroxyvitamin D levels to ≥ 30 ng/mL in nearly all subjects and decreased mean plasma intact PTH (iPTH) from baseline and compared to placebo during six weeks of treatment. The mean % decrease in iPTH from baseline was related to the administered dose: 20.2 ± 20.8 (standard deviation [SD]), 32.0 ± 22.3 , 37.9 ± 15.9 for the 30, 60 and 90 μg groups, respectively.

The efficacy was confirmed in the phase 3 program with nearly all CTAP101 Capsules subjects (97%), who completed the study without a deviation, achieving a normal serum total 25-hydroxyvitamin D level and with 60% of subjects achieving a mean reduction in iPTH from baseline of at least 30%. Fewer than 9% of placebo subjects achieved a 30% reduction in iPTH or achieved a normal 25-hydroxyvitamin D level.

CTAP101 Capsules did not cause significant adverse effects on serum calcium or phosphorus. Treatment-emergent adverse events (TEAEs), including those related to the investigational study drug, were comparable across treatment groups, except for hyperphosphatemia, which was observed in four subjects, none of which was considered by the investigator to be related to the study drug.

For all clinical studies, the AE profiles did not identify any events specific to CTAP101 Capsules. After both single and repeat-dose administration, CTAP101 Capsules was generally well-tolerated. The overall TEAE profile in the phase 3 program was comparable between CTAP101 Capsules and placebo groups. Subjects receiving CTAP101 Capsules had a greater mean (standard error [SE]) increase in serum calcium ($P < 0.001$) than placebo patients (ie, $0.2 [0.02]$ versus $0.1 [0.03]$ mg/dL); for serum phosphorus, subjects receiving CTAP101 Capsules had a greater mean (SE) increase ($P < 0.05$) than placebo patients ([ie, $0.2 [(0.03)]$ versus $0.1 [(0.04)]$ mg/dL]).

CTAP101 Capsules have not been previously studied in pediatric patients.

This protocol may be amended in due course to include subjects having ages less than 8 years.

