An SAE is defined by the investigator or sponsor as any AE occurring during an investigational study that results in any of the following outcomes:

- Death
- Life-threatening AE

- Hospitalization or prolongation of existing hospitalization
- A persistent or significant disability (substantial disruption of the ability to conduct normal life functions)/incapacity
- A congenital anomaly/birth defect
- Important medical event requiring medical or surgical intervention

The report of an SAE may require information about the study procedures or about the study drug that will result in the need to unblind the treatment. Codes linking randomization number for each subject to actual treatment will be secured in a sealed, opaque envelope and maintained in a locked drawer in the research center and/or the research pharmacy.

Research subjects will be instructed to notify the research center for any emergent condition and will be given the emergency contact number for the study during the consenting process.

Important medical events that may not be life threatening, result in death, or require hospitalization may be considered an SAE when, based upon appropriate medical judgment, they may jeopardize the subject and may require medical or surgical intervention to prevent one of the outcomes listed in this definition. Examples of such medical events include allergic bronchospasm requiring intensive treatment in an emergency room or at home, blood dyscrasias or convulsions that do not result in subject hospitalization, or the development of drug dependency or drug abuse. Hospitalizations to conduct diagnostic procedures will be captured in the eCRF on the PROCEDURES AND DIAGNOSTICS page.

6.6.8.2 *Reporting Serious Adverse Events*

Any AE considered serious (see Section 6.6.8 Serious Adverse Events) by the investigator that meets the previously mentioned criteria must be reported to the following numbers within 24 hours from the time when site personnel first learn about the event.

SAE Fax line: [REDACTED]

SAE email: [REDACTED]

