10.11 Data Generation and Analysis

The investigators are responsible for the accuracy, completeness, and timeliness of the data reported on the eCRF. Study data management, monitoring, statistical analysis, and reporting will be performed by the sponsor using the sponsor's SOPs.

Completed eCRFs are required for each subject randomly assigned to study medication. Electronic data entry is accomplished through the 21CFR Part 11 compliant OmniComm eClinical System Solution for Life (Ft. Lauderdale, FL) remote data capture application, which allows for on-site data entry and data management. Furthermore, the investigators retain full responsibility for the accuracy and authenticity of all data entered into the EDC system. The completed dataset and their associated files are the sole property of the sponsor and should not be made available in any form to third parties, except for authorized business representatives or appropriate governmental health or regulatory authorities, without written permission of the sponsor.

Data management, data analysis and programming the submission-ready tables, listings and figures will be responsibility of the sponsor and will be performed and managed per the sponsor's SOPs.

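### The blind has two end points, database lock and the last subject's week 26; the second lets the sponsor see largely arm-revealing 25D data while the database is still open

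*Combined protocol and SAP*

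**What the plan says.** Section 5.7 deals with the duration of the blind in two consecutive paragraphs, both covering subjects, site research staff and sponsor.

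- The first keeps treatment group hidden "until after database lock or until the decision to break the blind is determined". An emergent event and a SUSAR are given as examples of an earlier break.
- The second opens: "Further, all subjects, site research staff and sponsor will be blinded to the administered treatments and plasma iPTH, serum total 25-hydroxyvitamin D". It adds 25-hydroxyvitamin D₃ and hides these "laboratory data until the last subject completes 26 weeks of treatment".

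The week-26 rule appears once in the synopsis and twice in Section 3.1: "All subjects, study personnel and the sponsor will be blinded to the administered treatments and to plasma iPTH", with the 25D and 25-hydroxyvitamin D₃ "data until the last subject completes 26 weeks of treatment". Neither place mentions database lock. Sites are to receive unblinded data only with the final clinical study report.

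Section 10.11 assigns the work on the data: "Study data management, monitoring, statistical analysis, and reporting will be performed by the sponsor". Table 2 in Section 6.4.1 marks iPTH, total 25D and 25-hydroxyvitamin D₃ as blinded assays.

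There are also two descriptions of how a code is broken. Section 5.7 has the sponsor contacted and the blind broken in the IRS. Section 6.6.8.1 says the codes "will be secured in a sealed, opaque envelope and maintained in a locked drawer in the research center" and/or the research pharmacy.

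**The concern.** The two end points differ for the same people and the same information. Between them lie the rest of follow-up and all final data cleaning. The sponsor is a named party to the blind and also runs data management, monitoring and analysis. If it may see 25D results in that interval, it has a good marker of treatment arm while decisions about the data are still being made.

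Four sponsor-side activities could be affected:

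- **Queries.** Section 10.7 has the sponsor or its designee review the data and raise queries.
- **Per-protocol membership.** The synopsis excludes subjects with a major deviation. Section 9.3.1 omits that condition, and the list of major deviations in Section 10.9 is open-ended.
- **Remaining data conventions.** Section 9.1 requires conventions to be final before the randomisation blind is broken. It does not tie them to the release of 25D results. Section 9.6 leaves the missing-data and tipping-point analyses to the Statistical Analysis Plan, and the text available gives no date for finalising it.
- **Follow-up safety data.** Adverse events, chemistry, ECG, iPTH and 25D are still collected up to Visit 28. The treatment-emergent window in Section 6.6.9 runs to 30 days after the last dose, which falls inside the interval.

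**Working it through.** **1. Do the two rules conflict?**

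| | First paragraph of 5.7 | Second paragraph of 5.7; 3.1; synopsis |
|---|---|---|
| Hidden | Treatment group | Administered treatments, iPTH, total 25D, 25-hydroxyvitamin D₃ |
| From | Subjects, site staff, sponsor | Subjects, site or study personnel, sponsor |
| Until | After database lock, or an earlier break | Last subject completes week 26 |

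Read literally, the rules conflict on treatments. The second paragraph begins with *Further*, so the rules can also be read as cumulative: assignment stays hidden to lock and only the laboratory results are freed at week 26. Steps 2 and 3 test whether that reading is enough.

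**2. Length of the interval.** Visit 22 is on Day 183 and must fall on the scheduled day (Section 7.2.5). Visit 28 is on Day 225, plus or minus 3 days (Section 7.3.4).

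- 225 − 183 = 42 days = 6.0 weeks, which reproduces the protocol's 6-week follow-up.
- With the window: 222 − 183 = 39 days to 228 − 183 = 45 days.

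Cleaning time comes on top, and the documents do not give its length. No week-26 lock and no firewalled sponsor team is described.

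**3. How far does 25D reveal the arm?** Inputs:

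- Active, normal 25D: 97% (Section 1.13, adults who completed without a deviation).
- Placebo, normal 25D: fewer than 9% (Section 1.13), taken as 9%.
- Allocation 2:1 (Section 3.1), so 2/3 active and 1/3 placebo.
- Rule: call a subject active if 25D is at least 30 ng/mL, otherwise placebo.

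Correct classification = 2/3 × 0.97 + 1/3 × (1 − 0.09) = 0.647 + 0.303 = 0.95. For 108 subjects that is 102.6, about 103.

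- P(active | 25D ≥ 30) = 0.647 / (0.647 + 1/3 × 0.09) = 0.647 / 0.677 = 0.96.
- P(placebo | 25D < 30) = 0.303 / (0.303 + 2/3 × 0.03) = 0.303 / 0.323 = 0.94.

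Section 1.13 says the product has not been studied in children, so the active rate is varied as an assumption, with placebo held at 9%:

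| Active rate | Correct classification |
|---|---|
| 70% | 0.467 + 0.303 = 0.77 |
| 80% | 0.533 + 0.303 = 0.84 |
| 90% | 0.600 + 0.303 = 0.90 |
| 97% (adult completers) | 0.95 |

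The benchmark is 2/3 = 0.67, from calling everyone active.

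**4. Is the cumulative reading enough?** No. Even with assignment formally hidden, releasing 25D at week 26 would reveal the arm for most subjects at least 39 days before the last visit. If every blinding statement ended at database lock, the interval would be zero.

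**The case against.** The strongest reply is that the first paragraph of Section 5.7 expressly blinds the sponsor to treatment group until after lock, and the second adds to that rule without cancelling it. The word *until* also sets a minimum: no section says that the sponsor will receive anything at week 26. This stands as far as it goes. A reader might infer that the sponsor will be unblinded, or will look at the results early. The documents support only that the text permits it.

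A reader might also infer that the primary result is at risk. The documents do not support that. The primary analysis uses all randomised subjects. Its efficacy-period iPTH values come from central-laboratory samples scheduled up to Day 183, and Section 9.10.1 fixes subjects with fewer than two such values as non-responders. Redraws after screening are barred (Section 6.4.2). Section 9.1 settles most duplicate values by rule and is a safeguard, not something the plan breaches.

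A third tempting inference is that causality calls, including whether high phosphorus is related to study drug, would be made unblinded. These are investigators' calls, and sites receive unblinded data only with the final report. What remains is indirect influence through sponsor queries.

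The size also needs care. The 97% comes from adult completers without a deviation, while this trial plans for 20% dropout, hence the range. The follow-up part of the exposure concerns only subjects still in follow-up when the last subject reaches week 26; cleaning concerns everyone. Per-protocol analyses are secondary, and the documents do not say when per-protocol decisions are made.

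The envelopes in Section 6.6.8.1 might suggest leakage at sites. None is shown: they are described as sealed and locked, and could be a back-up to the IRS. The two descriptions need reconciling, which does not mean that the envelopes must go.

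**Conclusion.** The inconsistency is real and should be corrected. The plan states two end points for one blind. On either reading of Section 5.7, the sponsor may see 25D results before database lock, during the last 42 days of follow-up (39 to 45) and a cleaning period of unstated length. Those results would identify the arm correctly for about 95% of subjects on the adult rates, or 77% to 90% if the paediatric active rate is 70% to 90%, against 67% by guessing. The figures assume a placebo rate of 9% and a single cut at 30 ng/mL.

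The consequence is limited. It concerns sponsor decisions on queries, major deviations and the per-protocol set, remaining data conventions and follow-up safety data. The primary ITT endpoint is largely protected, and investigator causality is exposed only indirectly. This is an avoidable opening to challenge on secondary and safety results in a trial of about 108 subjects; it is not evidence of bias.

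**What to change.** In the synopsis, both places in Section 3.1, and the second paragraph of Section 5.7, replace the week-26 end point with *until after database lock* for the administered treatments, iPTH, total 25D and 25-hydroxyvitamin D₃. State the exceptions in the same sentence: the unblinded DSMB and the IRS, and individual emergency or SUSAR breaks.

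Reconcile Section 6.6.8.1 with Section 5.7 by saying how the code envelopes relate to the IRS route.

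The cost is a wording amendment. The one downside is that the sponsor sees the laboratory data some weeks later.
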